			
 - If still no improvement within 2 to 3 days despite IV methylprednisone at 2 to 4 mg/kg/day, promptly start immunosuppressive therapy such as tumor necrosis factor (TNF) inhibitors (eg, infliximab at 5 mg/kg IV once, may be repeated at 2 and 6 weeks after initial dose at the discretion of the treating provider or relevant practice guidelines). Caution: It is important to rule out sepsis and refer to infliximab label for general guidance before using infliximab. Consider, as necessary, discussing with Clinical Study Lead.
	
Grade 3 or 4 (Grade 3: severe symptoms; limiting self-care ADL; oxygen indicated) (Grade 4: life-threatening respiratory compromise; urgent intervention indicated [eg, tracheostomy or intubation])
	Permanently discontinue study drug/study regimen.	
For Grade 3 or 4 (severe or new symptoms, new/worsening hypoxia, life-threatening):
 
 - Promptly initiate empiric IV methylprednisolone 1 to 4 mg/kg/day or equivalent. - Obtain Pulmonary and Infectious Disease consults; consider discussing with Clinical Study Lead, as needed. - Hospitalize the patient. - Supportive care (eg, oxygen). - If no improvement within 2 days, additional workup should be considered and prompt treatment with additional immunosuppressive therapy such as TNF inhibitors (eg, infliximab at 5 mg/kg IV, maybe repeated at 2 and 6 weeks after initial dose at the discretion of the treating provider or relevant practice guidelines). Caution: rule out sepsis and refer to infliximab label for general guidance before using infliximab.

Diarrhea/Colitis Large intestine perforation/Intestine perforation
	Any Grade	General Guidance	
For Any Grade:
 
 - Monitor for symptoms that may be related to diarrhea/enterocolitis (abdominal pain, cramping, or changes in bowel habits such as increased frequency over baseline or blood in stool) or related to bowel perforation (such as sepsis, peritoneal signs, and ileus). - When symptoms or evaluation indicate a perforation is suspected, consult a surgeon experienced in abdominal surgery immediately without any delay. - Permanently discontinue study drug for any grade of intestinal perforation - Patients should be thoroughly evaluated to rule out any alternative etiology (eg, disease progression, other medications, or infections),

Date:

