			
including testing for clostridium difficile toxin, etc.
 
 - Steroids should be considered in the absence of clear alternative etiology, even for low-grade events, in order to prevent potential progression to higher grade event, including perforation. - Use analgesics carefully; they can mask symptoms of perforation and peritonitis.
	
Grade 1 (stool frequency of <4 over baseline per day)
	
No dose modifications.
	
For Grade 1:
 
 - Monitor closely for worsening symptoms. - Consider symptomatic treatment, including hydration, electrolyte replacement, dietary changes (eg, American Dietetic Association colitis diet), and loperamide and other supportive care measures. - If symptoms persist consider checking lactoferrin; if positive treat as Grade 2 below. If negative and no infection, continue Grade 1 management

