	
Grade 2 (Diarrhea: stool frequency of 4 to 6 over baseline per day) (Colitis: abdominal pain; mucus or blood in stool) (Perforation: symptomatic; medical intervention indicated*) *”medical intervention” is not invasive
	
Hold study drug/study regimen until resolution to Grade \leq1
 
 • If toxicity improves to Grade \leq1, then study drug/study regimen can be resumed after completion of steroid taper (<10mg prednisone, or equivalent). 	
For Grade 2:
 
 - Consider symptomatic treatment, including hydration, electrolyte replacement, dietary changes (eg, American Dietetic Association colitis diet), and loperamide and/or budesonide. - Promptly start prednisone 1 to 2 mg/kg/day PO or IV equivalent. - If event is not responsive within 2 to 3 days or worsens despite prednisone at 1 to 2 mg/kg/day PO or IV equivalent, gastrointestinal (GI) consult should be obtained for consideration of further workup, such as imaging and/or colonoscopy, to confirm colitis and rule out perforation, and prompt treatment with IV methylprednisolone 2 to 4 mg/kg/day started. - If still no improvement within 2 to 3 days despite 1 to 2 mg/kg IV methylprednisolone, promptly start immunosuppressives such as infliximab at 5 mg/kg IV, may be repeated at 2 and 6 weeks after initial dose at the discretion of the treating provider or relevant practice guidelines. Caution: it is important to rule out bowel perforation and refer to infliximab label for general guidance before using infliximab. - If perforation is suspected, consult a surgeon experienced in abdominal

Date:

			
surgery immediately without any delay.
 
 – Consider, as necessary, discussing with Clinical Study Lead if no resolution to Grade ≤1 in 3 to 4 days.

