	
Grade 3 or 4 (Grade 3 Diarrhea: stool frequency of ≥7 over baseline per day; Grade 4 Diarrhea: life threatening consequences) (Grade 3 Colitis: severe abdominal pain, change in bowel habits, medi-cal intervention indicated, peritoneal signs; Grade 4 Colitis: life-threatening consequences, urgent intervention indicated) (Grade 3 Perforation: severe symptoms, elective* operative intervention indicated; Grade 4 Perforation: life-threatening consequences, urgent intervention indicated) *This guidance anticipates that Grade 3 operative interventions of perforations are usually not elective
	
Grade 3
 
 – For patients treatet with durvalumab monotherapy, hold study drug/study regimen until resolution to Grade ≤1; study drug/study regimen can be resumed after completion of steroid taper (<10 mg prednisone per day, or equivalent). – For patients treated with durvalumab in combination with other products (not tremelimumab), decision to be made at the discretion of the study investigator, in discussion with AstraZeneca Clinical Study Lead. – For p atient s t reat ed with durvalumab in combination with tremelimumab or tremelimumab monotherapy. Permanently discontinue study drug for 1) Grade 3 diarrhea colitis or 2) Any grade large intestine perforation in any patient treated with immune checkpoint inhibitor (ICI). 	
For Grade 3 or 4:
 
 – Promptly initiate empiric IV methylprednisolone 1 to 2 mg/kg/day or equivalent. – Monitor stool frequency and volume and maintain hydration. – Urgent GI consult and imaging and/or colonoscopy as appropriate. – If still no improvement within 2 days continue steroids and promptly add further immunosuppressant agents (e.g., infliximab at 5 mg/kg IV, may be repeated at 2 and 6 weeks after initial dose at the discretion of the treating provider or relevant practice guidelines). Caution: Ensure GI consult to rule out bowel perforation and refer to infliximab label for general guidance before using infliximab. If perforation is suspected, consult a surgeon experienced in abdominal surgery immediately without any delay.

Date:

		
Grade 4
 
 – Permanently discontinue study drug/study regimen. 	

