
Isolated AST or ALT >2.0×baseline and ≤12.5×ULN, if elevated>ULN at baseline
	
elevation in the row below. If toxicity improves to AST or ALT ≤5.0xULN, resume study drug/study regimen after completion of steroid taper (<10mg prednisone or equivalent).
 
 • Permanently discontinue study drug/study regimen for any case meeting Hy’s law criteria, in the absence of any alternative cause.^b 	
Recommend consult hepatologist; consider abdominal ultrasound, including Doppler assessment of liver perfusion.
 
 – Consider, as necessary, discussing with Clinical Study Lead. – If event is persistent (>2 to 3 days) or worsens, and investigator suspects toxicity to be an imAE, start prednisone 1 to 2 mg/kg/day PO or IV equivalent. – If still no improvement within 2 to 3 days despite 1 to 2 mg/kg/day of prednisone PO or IV equivalent, consider additional workup. If still no improvement within 2 to 3 days despite 2mg/kg/day of IV methylprednisolone, consider additional abdominal workup (including liver biopsy) and imaging (i.e., liver ultrasound), and consider starting additional immunosuppressants. (e.g., mycophenolate mofetil 0.5 – 1 g every 12 hours then taper in consultation with hepatology consult or relevant practice guidelines). Discuss Clinical Study Lead if mycophenolate mofetil is not available. Infliximab should NOT be used.

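### Table 4 orders a permanent stop for any intestinal perforation, but its Grade 2 row grades perforation by name and lets both arms resume; at Grade 3 the stop is misplaced and too narrow

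*Combined protocol and SAP*

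**What the plan says.** Section 11.1, Table 4 handles diarrhea, colitis and intestinal perforation as one event, with an Any Grade entry followed by grade rows.

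- **Any Grade.** The Toxicity Management column says "Permanently discontinue study drug for any grade of intestinal perforation". The Dose Modifications cell beside it is only a general-guidance label.
- **Grade 1.** The definition concerns diarrhea alone: "Grade 1 (stool frequency of <4 over baseline per day". No Grade 1 perforation is defined.
- **Grade 2.** The severity cell lists "Perforation: symptomatic; medical intervention indicated". The dose cell says to hold until Grade 1 or below, and "then study drug/study regimen can be resumed after completion of steroid taper (<10mg prednisone, or equivalent". It does not distinguish between arms or mention perforation.
- **Grade 3.** The severity cell lists "Grade 3 Perforation: severe symptoms, elective* operative intervention indicated". For durvalumab monotherapy the dose cell says to hold until Grade 1 or below, after which "study drug/study regimen can be resumed after completion of steroid taper (<10 mg prednisone per day, or equivalent". The bullet for tremelimumab-containing treatment orders a permanent stop for Grade 3 diarrhea or colitis and, as its second item, for "Any grade large intestine perforation in any patient treated with immune checkpoint inhibitor (ICI".
- **Grade 4.** Permanent discontinuation.

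**The concern.** A clinician managing a perforation will look up its grade and read the dose cell in that row. At Grade 2 the row confirms that perforation belongs there and then gives a route back to treatment. The Any Grade entry removes that route. Both instructions cannot hold for the same patient, and the table gives no order of precedence.

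What is at stake is safe dosing after a rare but serious event. Section 11.4.3, on gastrointestinal disorders, says that colon perforation under tremelimumab is rare, may need surgery and can be fatal if badly managed. The Any Grade stop takes the decision out of the clinician's hands, while the Grade 2 dose cell gives it back.

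**Working it through.** There is no figure to reproduce. The check compares, instruction by instruction, what the Any Grade entry requires with what each dose instruction permits.

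**Step 1. Which instructions count.** The rows that name perforation contain five dose instructions: Grade 2; Grade 3 durvalumab monotherapy; Grade 3 durvalumab with products other than tremelimumab; Grade 3 with tremelimumab; and Grade 4. The third applies to neither arm, so 5 − 1 = 4 remain.

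**Step 2. Comparison with the Any Grade stop.**

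| Instruction | Applies to | What it says for perforation | Against the Any Grade stop |
|---|---|---|---|
| Grade 2 | Both arms | Hold, then resume after taper; no exception | Conflicts |
| Grade 3, durvalumab monotherapy | Arm 1 | Hold, then resume after taper; a later clause in the same cell stops large intestine perforation if read literally | Conflicts in part |
| Grade 3, with tremelimumab | Arm 2 | Permanent stop, large intestine only | Narrower |
| Grade 4 | Both arms | Permanent stop | Agrees |

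The four split as 1 + 1 + 1 + 1.

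**Step 3. Does the Grade 3 clause resolve the conflict?** "Any grade large intestine perforation in any patient treated with immune checkpoint inhibitor (ICI" has wide wording. Durvalumab is an anti-PD-L1 antibody and so an immune checkpoint inhibitor, which brings Arm 1 within the clause. The words also reach Grade 2. Three things limit it. It is the second item of a bullet headed for tremelimumab, so an Arm 1 reader has reason to pass over it. It lies in the Grade 3 cell, so a reader in the Grade 2 row does not meet it. It names only the large intestine, whereas the Any Grade entry covers all intestinal perforation. It confirms the intended rule but leaves the Grade 2 permission standing.

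**Step 4. Does the rest of the table settle it?** The general rules at the head of Table 4 base permanent stops on grade and add two further conditions: failure to reduce corticosteroids within 12 weeks, and Grade 3 recurrence of an earlier treatment-related event. Perforation is neither, and the general Grade 2 rule also permits resumption.

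**Step 5. Is this simply how the table is laid out?** Partly. Two other Any Grade stops stand in the Toxicity Management column: confirmed severe cutaneous reactions (rash row) and transverse myelitis (neurotoxicity row). Their grade rows also hold and resume without an exception, but they do not name the stopped event. The perforation rows do. Clearer forms exist in the same table: a hepatitis hold/resume cell carries its own stop, "Permanently discontinue study drug/study regimen for any case meeting" Hy's law criteria, and the myocarditis row puts its Any Grade stop in the dose column.

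**The case against.** The best reply is that the rule is already written. The Any Grade entry is specific to perforation, stands directly above the grade rows, and its wording must include Grades 2 and 3. An event-specific stop would normally override hold/resume text shared with diarrhea and colitis. That text fits perforation poorly anyway: it resumes at Grade 1 or below, where the table defines only stool frequency, and Grade 2 management treats perforation as something to rule out, with immediate surgical consultation if suspected. This stands as evidence of intent. It does not remove the Grade 2 conflict, because that row grades perforation by name and then permits resumption.

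The second reply is that other text narrows the risk. The general guidance in Table 4 refers to a 28-day taper, and Section 11.1 discontinues patients who miss 28 or more consecutive days because of drug-related events. Section 13.0 lists a delay beyond 28 days as a possible reason for discontinuation, and bars further dosing when the investigator or sponsor judges an event a contraindication. These safeguards are real but partial: the Section 11.1 rule allows exceptions approved by the Principal Investigator, and the contraindication rule rests on judgment.

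Two stronger readings are tempting. A reader might infer that Arm 1 patients with a Grade 3 perforation may resume with no exception anywhere. The documents do not support that, since the same dose cell stops large intestine perforation in any checkpoint-inhibitor patient. A reader might also infer that placing the stop in the Toxicity Management column is itself an error. The rash and neurotoxicity rows show that this placement recurs in the table.

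**Conclusion.** The inconsistency is real and minor. At Grade 2 the conflict is direct and applies to both arms. At Grade 3 what remains is a stop placed under the wrong bullet, plus no coverage in that cell of perforation outside the large intestine; there the Any Grade entry alone supplies the rule.

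This rests on the wording of one table and on the assumption that some readers will act on the dose cell of a grade row without applying the Any Grade entry above it. The evident intent is a permanent stop, and most clinicians would follow it. The documents give no perforation rate for this population, so no number of affected patients can be claimed. Sample size, error rates and efficacy results do not change.

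**What to change.** Make two wording changes in Table 4 at the next amendment:

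1. In the Grade 2 Dose Modifications cell, add: *except intestinal perforation of any grade: permanently discontinue*.
2. Take the perforation stop for checkpoint-inhibitor patients out of the Grade 3 tremelimumab bullet. Make it a stand-alone line in the Any Grade Dose Modifications cell, covering all intestinal perforation in both arms.

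The second change also settles the Grade 3 monotherapy question, because the stop would then stand in the dose column for every grade and both arms. The cost is a few words in one table, with no new visits, procedures or data.

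### In Table 4, the Grade 2 colitis cell and one hepatitis cell judge steroid failure on a methylprednisolone course that the same cell does not order

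*Combined protocol and SAP*

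**What the plan says.** Section 11.1, Table 4, sets out stepwise steroid management for each immune-mediated reaction.

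**Diarrhea/colitis, Grade 2.** The first steroid step is "Promptly start prednisone 1 to 2 mg/kg/day PO or IV equivalent". If there is no response in 2 to 3 days, or the event worsens, the cell asks for a GI consult and "prompt treatment with IV methylprednisolone 2 to 4 mg/kg/day started". The next bullet is "If still no improvement within 2 to 3 days despite 1 to 2 mg/kg IV methylprednisolone, promptly start immunosuppressives", with infliximab as the example.

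**Hepatitis, the band for AST or ALT above 5 to 8 times ULN if normal at baseline, or above 2 times baseline up to 12.5 times ULN if elevated.** For a persistent or worsening event that the investigator suspects is immune-mediated, the instruction is to "start prednisone 1 to 2 mg/kg/day PO or IV equivalent". The next step is "If still no improvement within 2 to 3 days despite 1 to 2 mg/kg/day of prednisone PO or IV equivalent, consider additional workup". The one after that is "If still no improvement within 2 to 3 days despite 2mg/kg/day of IV methylprednisolone, consider additional abdominal workup", together with considering a further immunosuppressant such as mycophenolate.

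**The concern.** In an escalation ladder, each failure test should refer to the treatment that the previous rung started. In these two cells it does not.

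In the colitis cell, the word *still* ties the trigger to the step before it, yet the dose named is not the dose that step starts. The first rung also permits an IV equivalent of prednisone at 1 to 2 mg/kg/day. If that is given as methylprednisolone, the patient can be read on day 2 to 3 as meeting two bullets at once: one raises the steroid, the other starts infliximab.

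In the hepatitis cell, the reader has to infer a step that is not written.

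The steroid course also feeds into treatment received. For Grade 2 colitis, study drug resumes only after the taper. Failure to get down to 10 mg/day of prednisone within 12 weeks means permanent discontinuation. Missing 28 or more consecutive days for drug-related events removes the patient from the study, subject to exceptions by the Principal Investigator. In Arm 2 both agents are held together. In the combination study summarised in Section 3 (D4190C00006), colitis (9.8%) and diarrhea (7.8%) were the only serious events above 5%, and colitis was the leading treatment-related cause of discontinuation (7 subjects).

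**Working it through.** The plan states no statistical figure on this point, so there is none to reproduce. The check compares, cell by cell, the steroid course started with the course on which failure is judged.

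| Table 4 cell | Methylprednisolone started | Dose named in the failure test | Match |
|---|---|---|---|
| Colitis, Grade 2 | 2 to 4 mg/kg/day | 1 to 2 mg/kg, no per-day unit | No |
| Colitis, Grade 3 or 4 | 1 to 2 mg/kg/day | none named | No conflict |
| Hepatitis, lower hold band (above) | none; prednisone 1 to 2 mg/kg/day only | 2 mg/kg/day IV | No |
| Hepatitis, next band up to 20 times ULN | 1 to 2 mg/kg/day | 1 to 2 mg/kg/day | Yes |
| Pneumonitis, Grade 2 | 2 to 4 mg/kg/day | 2 to 4 mg/kg/day | Yes |
| Myocarditis, Grade 2 to 4 | 2 to 4 mg/kg/day | 2 to 4 mg/kg/day | Yes |
| Myositis, Grade 2 and Grade 3 or 4 | 2 to 4 mg/kg/day | 2 to 4 mg/kg/day | Yes |

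**Colitis, size of the mismatch.** Trigger over start is 1/2 = 0.5 at the lower limit and 2/4 = 0.5 at the upper limit. The ranges share only the value 2 mg/kg. For the 75 kg reference weight used in the fixed-dosing rationale, and reading the trigger as a daily dose (an assumption, since the unit is absent):

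- started: 75 × 2 = 150 to 75 × 4 = 300 mg/day
- named in the trigger: 75 × 1 = 75 to 75 × 2 = 150 mg/day

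**Colitis, which figure was meant.** The pneumonitis Grade 2 cell has the same ladder and tests failure with "If still no improvement within 2 to 3 days despite IV methylprednisone at 2 to 4 mg/kg/day", which would suggest the higher range. The colitis Grade 3 or 4 cell, directly below, starts the lower range. The two neighbours point in different directions, so the table does not resolve the question.

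**Hepatitis.** Steps in the cell that start a named methylprednisolone course: 0. Steps that judge its failure: 1, namely "If still no improvement within 2 to 3 days despite 2mg/kg/day of IV methylprednisolone". The cell already has a separate failure step for prednisone, so the second test is not a restatement of the first. The general guidance at the top of Table 4 raises prednisone to 2 to 4 mg/kg/day, but only for symptoms that recur or worsen during taper, so it does not supply the missing step.

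**Patients affected.** Study D4190C00006 reports treatment-related diarrhea in 27.5% (7.8% at Grade 3 or above) and colitis in 11.8% (8.8% at Grade 3 or above). By subtraction, Grade 1 or 2 is 27.5 − 7.8 = 19.7% for diarrhea and 11.8 − 8.8 = 3.0% for colitis. On 40 patients that is 0.197 × 40 = 7.9 and 0.030 × 40 = 1.2, and the two groups may overlap. These figures still mix Grade 1 with Grade 2, come from patients with lung cancer, and pool cohorts given tremelimumab at 3 and 10 mg/kg, where Section 3 says colitis was more common. The share of Grade 2 events refractory to steroids is given nowhere. No count of affected patients follows.

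**The case against.** The strongest reply is that the consequences are small.

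- **Colitis.** A patient who has not improved on 2 to 4 mg/kg/day has also not improved despite 1 to 2 mg/kg. For that patient both wordings lead to the same next step after the same 2 to 3 days. This stands. It does not help the patient treated intravenously on the first rung, for whom the two bullets compete.
- **Hepatitis.** A reader might infer that the patient can never reach further immunosuppression. The documents do not support that. The general guidance says stronger immunosuppressives should be considered when systemic steroids fail. Worsening enzymes move the patient to the next band, which is consistent. The cell recommends a hepatology consult, and its last step is only a suggestion to consider. The cover is partial, though. The general statement names no dose or timing, and the next band serves patients who worsen, not those who simply fail to improve.
- **Frequency.** A reader might take hepatitis to be among the most frequent serious toxicities of the combination. The Section 3 safety summary supports that for colitis and diarrhea only.
- **Status of the text.** Section 11.1 calls its dose-delay and reduction instructions guidelines, and Table 4 presents its management of these events as recommended. The colitis cell also suggests discussion with the Clinical Study Lead if the event has not resolved in 3 to 4 days. Judgment will often bridge the gap. That limits the harm but does not remove the contradiction.

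**Conclusion.** The point holds as a drafting contradiction in two cells of current, operative rescue text. In the Grade 2 colitis cell the trigger range is exactly half the started range at both limits and lacks its time unit. In the one hepatitis band identified, failure is judged on a course that no step in that cell starts; the other hepatitis bands are not affected.

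The likely effect is inconsistent steroid dosing and escalation in a small number of patients. The number cannot be derived: all-grade rates from the earlier combination study should not be turned into a count of Arm 2 patients, because neither the Grade 2 share nor the refractory share is given and the cohorts included higher tremelimumab doses.

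Two stronger inferences should be resisted. The pneumonitis row does not show that the higher colitis dose was intended, since the adjacent colitis row starts the lower one. And nothing here touches sample size, power, type I error or the response and PFS decision rules. The conclusion rests only on reading each cell's steps in the order printed.

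**What to change.** The sponsor and its safety physicians should:

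1. reconcile the two Grade 2 colitis sentences with each other, and state the unit in both;
2. reconcile the steps of the affected hepatitis cell, so that the course on which failure is judged and the courses the cell starts agree.

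Which dose or step is retained is their clinical decision, and this review offers no view on it. The table heading carries a version date of 28 October 2021. If the table was transcribed from a source guideline, comparison with that source would show whether either discrepancy is a copying slip.

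The cost is two table-cell edits in an amendment. No change to the statistical section is needed.
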